3.2.3.6.9 Visits Past Month 48 (Visit 18)

Since this is an event-driven trial as described earlier in this document, the length of time a patient will be in the trial is unknown, and may extend past the 48 months detailed in the Study Flow Chart. For patients with visits past 48 Months, the following visits and procedures should occur.

- 3 month phone contacts (Months 51, 57, 63, etc.)

The same procedures performed at Month 45 (and similar visits) should be conducted. Please see section 3.2.3.6.6.

- 6 month clinic visits (Months 54, 66, etc.)

The same procedures performed at Month 42 (and similar visits) should be conducted. Please see section 3.2.3.6.3.

- Annual clinic visits (Months 60, 72, etc.)

The same procedures performed at Month 48 (and similar visits) should be conducted. Please see section 3.2.3.6.7.

3.2.3.6.10 End of Study Visit

While the exact timing for the end of the study is unknown and depends on the accumulation of a sufficient number of fracture events, it is estimated to be approximately 3 years after the end of enrollment. The SPONSOR will alert sites when the study will be terminated. At that point, all patients must be brought in for a final visit. Laboratory safety assessment, biomarkers and archive samples do not need to be obtained if less than 30 days have elapsed since the last collection. DXA scans do not need to be performed if less than 6 months have elapsed since the last scan was performed.

Product: MK-0822

24

Protocol/Amendment No.: 018-04

Sites will be asked to contact all patients by telephone to schedule the End of Study visits and to re-enforce the importance of this visit. Every effort should be made to ensure that all patients attend the End of Study Visit in the time pre-specified by the SPONSOR.

Table 3-8 lists the procedures to be performed at the final study visit.

Table 3-8

List of End of Study Procedures

Perform BMD at the total hip (and subregions) and lumbar spine [§] ^{††} Perform BMD at the distal forearm and total body [¶] Complete PE (including vital signs, height and weight) Perform lateral spine x-ray [§] Collect blood and urine for laboratory safety assessment [†] Collect blood and urine for lab efficacy assessment and archives [‡] Administer calcium questionnaire [#] Review diary card Perform tablet count for compliance (only for blinded study therapy) Review Adverse Experiences Concomitant Medication Review Perform Health Resource Utilization (if fracture has occurred) Plasma for proteomics archive
[†] Laboratory specimen for safety assessments need not be drawn in a fasted state. Do not need to be repeated if less than 30 days elapsed since prior draw. [‡] Specimens for efficacy test should only be collected in a 10% subset of patients. Archival specimens will be collected for all patients. All samples should be fasting specimens, and urine should be second morning void. Do not need to be repeated if less than 30 days elapsed since prior draw. [§] BMD to be performed if more than 6 months have elapsed since prior measurement was performed. Lateral spine x-ray to be performed if more than 3 months have elapsed since prior measurement was performed. Performed on all patients. [¶] Performed in 10% of patients. [#] Administer Calcium Questionnaire if more than 6 months have elapsed since the questionnaire was administered previously. ^{††} The same hip must be scanned as was used at baseline.

3.2.3.6.11 Post-study Telephone Call

Approximately 14 days after the last dose of blinded study therapy or study end/discontinuation, the Investigator will contact the patient by telephone to collect serious AE information.

Product: MK-0822

25

Protocol/Amendment No.: 018-04

3.2.3.7 Study Termination

Study termination will be the result of the basic scenarios described below:

- *Based upon the advice of the DMC on safety concerns.*
- *Inability to accrue the required number of fracture events.* The Steering Committee and SPONSOR will be monitoring the number of fractures reported during the study, and will advise the SPONSOR if they determine this situation has occurred. A plan for terminating the study will then be identified and communicated to the clinical centers.
- *Based on advice from the DMC if in the formal interim analysis, evidence is shown that odanacatib will be unable to demonstrate efficacy.*
- *Based on advice from the DMC for statistically significant treatment effect seen in one of the formal interim efficacy analyses as detailed in Section 3.5.*
- *Upon accruing the required number of fracture events necessary to test the study's hypotheses.* The Steering Committee and SPONSOR will be monitoring the number of fractures reported in the study, and will determine when the requisite number of fractures have occurred. Every effort should be made to ensure that all patients attend the final study visit in the time pre-specified by the SPONSOR.

3.2.3.8 Blinding/Unblinding

IVRS should be used for emergency unblinding treatment assignment in the event that this is required for patient safety. Every effort should be made to contact the Clinical Monitor prior to such unblinding; however the Investigator may unblind a patient for safety reasons without first contacting the Clinical Monitor. In the event that unblinding has occurred, the circumstances around the unblinding must be documented promptly, and the SPONSOR notified as soon as possible. Note that all patients who have been unblinded must be discontinued from the study.

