3.2.3.9.1 Discontinuation Rules

As in all clinical trials, patients will be discontinued from blinded study therapy if the investigator feels that the risk outweighs the benefit of participation for an individual patient. Additionally, the following discontinuation rules will be applied.

Product: MK-0822

26

Protocol/Amendment No.: 018-04

- If relationship of the adverse experience to study drug is demonstrated by de-challenge and re-challenge, and the adverse experience is considered severe in intensity, or is serious.
- If a patient has a normal lymphocyte count at baseline, and then during treatment, lymphocyte count falls below the lower limit of the normal range and remains below the normal range on at least 2 repeated measurements, at least 1 week apart, and lymphocyte count returns to the normal range after interruption of study drug.
- If a patient experiences excessive bone loss, defined as a loss at the lumbar spine or total hip of 7% or greater compared to baseline at any point in the trial.
- If a patient demonstrates:
 - Persistent elevations [$> 3 \times$ Upper Limit of Normal (ULN)] in aspartate aminotransferase (AST) or alanine aminotransferase (ALT) (2 consecutive readings at least 2 weeks apart) - OR -
 - Persistent elevations [$> 2 \times$ Upper Limit of Normal (ULN)] in total bilirubin (2 consecutive readings at least 2 weeks apart).
- If a patient begins a treatment regimen with a strong CYP3A4 inducer (e.g., rifampin [rifampicin], phenobarbital, barbiturates, carbamazepine, phenytoin, St. John's wort, nevirapine, efavirenz, etravirine) for a period longer than 6 months in duration.
- If a patient commences therapy with low-dose systemic estrogens for 6 months or more.
- If a patient begins treatment with bisphosphonates, strontium, or PTH, the SPONSOR must be contacted and blinded study therapy will likely be discontinued.

Patients will be followed for outcome through the end of the trial even if blinded study therapy is discontinued.

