3.2.3.10 Discontinuation/Withdrawal From The Study

Note that patients inappropriately randomized into the trial (i.e. those who do not meet entry criteria) may be discontinued from the study at the discretion of the SPONSOR. Patients who discontinue the study may be permitted to rejoin pending approval of the SPONSOR.

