3.5.4 Analysis Populations

For fracture endpoints a "Full-Analysis-Set" (FAS) population will be used. This will include all randomized patients, who took at least one dose of study medication, with follow-up from Randomization to study termination, without regard to protocol violations, compliance to study drug or early treatment discontinuation. Patients will be counted in the treatment group they were randomized to, irrespective of the treatment they actually received.

All available scans to determine morphometric vertebral fractures, will be used in the analyses. For morphometric fractures, a patient with no scan during the study will not be included in the FAS population. For the final analysis of clinical fractures, a calendar date (cut-off) will be determined when the pre-specified number of fracture events are seen. For the analysis of clinical fractures, patients who did not have a fracture by the time of the cut-off date will be censored at the cut-off date, unless they discontinued the study earlier, then they will be censored at the date of the last contact with the patient (either

Product: MK-0822

46

Protocol/Amendment No.: 018-04

telephone contact or study visit). Clinical fractures after the cut-off date will not be included in the analysis.

As a supportive approach, vertebral, non-vertebral and hip fracture analyses will also be performed based on the "Per-Protocol" (PP) population, to investigate the influence of missing data and protocol violators on the treatment effect. This approach excludes patients from the FAS population if they have important protocol deviations. Specific criteria to exclude a patient are identified in appendix 6.7, prior to unblinding of study database and will be based on a patient's compliance to study medication, the use of prohibited previous or concomitant medication, and the presence of secondary diagnoses which may influence the efficacy results. Data will be censored at the date of the last dose of study medication plus 30 days, for patients who did not have a clinical fracture by that time. The per-protocol analysis will not be performed if less than 10% patients (included in the FAS approach) are protocol violators.

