The number and percentage of patients with secondary diagnoses will be summarized by treatment group for each system organ class and preferred term, for terms with an incidence of at least 1% in one of the treatment groups. Similar summaries will be provided for all specific secondary diagnoses and for the number of patients with prior medications and for the number of patients with concomitant medications. Special attention will be paid to prior osteoporotic medications.

Study participants accounting will be examined by tabulation of the number of patients screened but not randomized (with the reason for not being randomized), the number of patients randomized, the number of patients completing the study, and the number of patients discontinuing the study early with the reasons for early discontinuation and the number of patients who discontinued treatment early with the reason for early termination. Since this is a pure Intention to Treat (ITT) study, patients are to be followed off-drug for the remainder of the study if they discontinue treatment early.

Definition of Compliance Measure

For each patient, two compliance measures will be calculated based on the prime therapy records provided in the eCRFs. The first one describes the compliance to treatment up to treatment discontinuation and the second during the complete study.

Compliance During the Treatment Period:

The compliance during the treatment period, until permanent discontinuation from treatment, will be defined as:

$$\begin{aligned} & \text{compliance during treatment period (\%)} \\ & = 100 * \frac{\text{actual number of days with double - blind treatment intake}}{\text{expected number of days with intake in treatment period}} \end{aligned}$$

The "actual number of days with double-blind treatment intake" refers to the number of days on which double-blind treatment was taken.

The "expected number of days with intake in treatment period" refers to the number of days during the treatment period on which a weekly tablet was to be taken, calculated as

Product: MK-0822

16

Protocol/Amendment No.: 018-04

the number of days from the study treatment start day to the date of the last treatment intake before the cut-off date for analysis divided by 7 (rounded upwards).

Compliance During the Complete Study:

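### Unblinded patients must leave the study, which conflicts with the protocol's own follow-up to trial end and may make their censoring informative

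*Protocol*

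**What the plan says.** On unblinding, Section 3.2.3.8 provides emergency code breaks through the interactive voice system when patient safety requires it, and "the Investigator may unblind a patient for safety reasons without first contacting the Clinical Monitor". The section ends: "Note that all patients who have been unblinded must be discontinued from the study". Appendix 6.7 (Blinding/Unblinding) expects emergency requests for a variety of reasons, adverse experiences among them. It says they will be kept to a minimum and reported in the Clinical Study Report.

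On follow-up, Section 3.2.3.9.1 states: "Patients will be followed for outcome through the end of the trial even if blinded study therapy is discontinued". Appendix 6.7 states: "Since this is a pure Intention to Treat (ITT) study, patients are to be followed off-drug for the remainder of the study". Section 3.5.4 defines the full analysis set (FAS) with follow-up from randomization to study termination, "without regard to protocol violations, compliance to study drug or early treatment discontinuation".

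On early leavers, Section 3.5.4 censors clinical-fracture times at the last contact. Section 3.5.5.1 censors morphometric vertebral fractures just after the last time point with a film.

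On ineligible patients, Sections 1.4, 2.2, 2.3 and 3.2.3.10 say that those randomized without meeting entry criteria "may be discontinued from the study at the discretion of the SPONSOR". Section 3.2.3.10 adds: "Patients who discontinue the study may be permitted to rejoin pending approval of the SPONSOR".

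**The concern.** The protocol keeps leaving therapy apart from leaving the study: Section 3.2.3.9 deals with the first and Section 3.2.3.10 with the second. The reference to the study in Section 3.2.3.8 therefore has to be read literally. A site that obeys it cannot also deliver follow-up to trial end for that patient.

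A code break is a post-randomization event that depends on the patient's clinical course, and possibly on treatment. If women whose code is broken differ afterwards in fracture risk or mortality, and if breaks differ between arms, censoring at last contact is not independent of outcome. The Cox model and the complementary log-log model both assume that it is. The FAS hazard ratios and the primary adverse-event comparison, which Section 3.5.5.2 runs to the cut-off or last contact, would carry that bias. The loss comes from a written rule and is avoidable, because the protocol already follows other patients off drug.

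**Working it through.** **1. The passages side by side**

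- A patient who stops blinded therapy is followed to the end of the trial (3.2.3.9, 3.2.3.9.1, Appendix 6.7).
- A patient whose code is broken must leave the study (3.2.3.8). No exception allows outcome follow-up.
- The FAS runs to study termination (3.5.4). It keeps an unblinded patient in the denominator, but only with data up to last contact.

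**2. What is collected after exit**

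- At exit, all end-of-study procedures are due (3.2.3.9). These include a spine film unless one was taken recently (3.2.3.6.10). Data up to that date are kept.
- Serious adverse events are collected for 14 days after the later of stopping treatment and leaving the study (3.4.5.1).
- Later serious events are reportable only if the investigator judges them related to the product and hears of them. Serious events already reported are followed for outcome (3.4.5.1).
- Nothing provides for collecting later fractures, other adverse events or unrelated deaths, unless the sponsor lets the patient rejoin (3.2.3.10).

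**3. The plan's event targets, as a base for size**

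Inputs from Section 3.5.5.4: two-sided alpha 0.04, power 90%, 1:1 allocation, hip relative risk 0.65, and placebo hip rate 1.8% at 3 years for the 1:3 mix.

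- Hazard ratio: HR = ln(1 − 0.65 × 0.018) / ln(1 − 0.018) = 0.648.
- Schoenfeld: events = 4 (z₀.₉₈ + z₀.₉₀)² / (ln HR)² = 4 (2.054 + 1.282)² / (ln 0.648)², giving 237. This is the plan's figure.
- Non-vertebral: placebo rate 0.25 × 11% + 0.75 × 8% = 8.75% at 2 years and relative risk 0.8 give HR 0.7925 and 824 events, again the plan's figure.

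No sample-size figure is in error on this point.

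**4. Power if hip events are lost and not replaced**

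The documents give no loss figure, so the percentages are assumptions. HR 0.648, alpha 0.04.

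| Hip events lost | Events left | Power |
|---|---|---|
| 0% | 237 | 90.1% |
| 0.5% | 235.8 | 89.9% |
| 1% | 234.6 | 89.8% |
| 2% | 232.3 | 89.5% |
| 5% | 225.15 | 88.5% |

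The trial is event-driven, so lost events would mainly lengthen it.

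**5. Sensitivity of the hip estimate to one-sided loss**

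Split 237 events at a simple ratio of 0.65: odanacatib 237 × 0.65 / 1.65 = 93.4, placebo 143.6. Remove k events from one arm only.

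| k | Lost from odanacatib: (93.4 − k) / 143.6 | Lost from placebo: 93.4 / (143.6 − k) |
|---|---|---|
| 1 | 0.643 | 0.655 |
| 3 | 0.629 | 0.664 |
| 5 | 0.615 | 0.673 |
| 10 | 0.580 | 0.699 |

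These are illustrations of the most unequal case. They do not predict the size or direction of bias.

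**The case against.** The strongest reply is that the follow-up promises concern patients who stop therapy, not those who leave the study. Section 3.5.4 foresees early leavers and keeps them in the FAS to last contact. Exit procedures are complete, patients may rejoin, and code breaks are to be few and reported.

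This limits the harm but does not remove the conflict. For unblinded patients the protocol itself turns a change in blinding status into loss of follow-up, and states no exception to its intention-to-treat principle. Rejoining is discretionary and sits awkwardly with a mandatory exit. Fewer code breaks means fewer losses, not less selective ones.

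The reply succeeds against several stronger readings that a reader might infer:

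- *The rule on ineligible patients is an equal contradiction and loses outcomes selectively.* Section 1.4 states it openly as an exception. Entry criteria are mainly pre-randomization facts, bone density and spine-film eligibility is confirmed centrally beforehand, and the sponsor is blinded. Selective loss is not shown. What stands is that the discretion has no criterion or time limit.
- *Code breaks follow serious events.* Section 3.2.3.8 speaks of patient safety and Appendix 6.7 of various reasons. Neither requires seriousness.
- *All later serious events and deaths are lost.* Section 3.4.5.1 keeps the 14-day window and later reporting of related serious events.
- *The number of missed fractures can be calculated.* No rate of code breaks or removals is given, and the two groups should not be pooled.
- *Blinded adjudication makes fractures immune to a code break.* Patients report fractures, and classification as osteoporotic draws on a description of how the fracture happened (3.4.1.3, 3.5.3). Knowledge of treatment could affect both.

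**Conclusion.** The point holds for unblinded patients. Section 3.2.3.8 cannot be followed together with Section 3.2.3.9.1, the intention-to-treat statement in Appendix 6.7 and FAS follow-up to study termination in Section 3.5.4. The resulting censoring follows a post-randomization, largely safety-driven event and may be informative for fractures, adverse events and deaths.

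The number of patients and the direction of bias cannot be derived from the documents. The effect on power is small, at most about 1.6 percentage points over the assumed range of 0.5% to 5% of hip events lost without replacement. The case therefore rests on possible bias and lost safety data, not on power or sample size. It assumes that sites apply the rule as written and that few unblinded patients are allowed back.

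The sponsor's discretion over ineligible patients is a secondary weakness: disclosed, but unbounded. The change is worth making because the conflict is plain and cheap to remove.

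**What to change.** 1. Reconcile Section 3.2.3.8 with Sections 3.2.3.9.1 and 3.5.4 and Appendix 6.7 by separating study therapy from outcome follow-up. State that unblinded patients remain in the study for fracture, x-ray, adverse-event and vital-status follow-up unless they withdraw consent.
2. Have the sponsor state separately what applies to the study therapy of unblinded patients. Section 3.2.3.8 contains only the study-level rule, so changing it would leave this unsaid. No therapy rule is proposed here.
3. Add a sensitivity analysis of the primary fracture endpoints that censors at the date of code break, because reporting and the account of fracture circumstances may change once treatment is known.
4. In Sections 1.4, 2.2, 2.3 and 3.2.3.10, state that ineligible randomized patients also stay in outcome follow-up unless consent is withdrawn. This preserves the FAS as defined.

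The cost is amendment wording, one additional analysis, and continued visits for what should be a small number of patients, as is already done for others off drug.

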3.2.3.9 Discontinuation/Withdrawal From Study Therapy

Patients who stop taking study drug prior to the end of the study and agree to continue evaluation and participation in the study must be followed off-drug for the duration of the trial. If a patient discontinues blinded study therapy and/or from study participation, all end of study procedures should be performed.

3.2.3.9.1 Discontinuation Rules

As in all clinical trials, patients will be discontinued from blinded study therapy if the investigator feels that the risk outweighs the benefit of participation for an individual patient. Additionally, the following discontinuation rules will be applied.

Product: MK-0822

26

Protocol/Amendment No.: 018-04

- If relationship of the adverse experience to study drug is demonstrated by de-challenge and re-challenge, and the adverse experience is considered severe in intensity, or is serious.
- If a patient has a normal lymphocyte count at baseline, and then during treatment, lymphocyte count falls below the lower limit of the normal range and remains below the normal range on at least 2 repeated measurements, at least 1 week apart, and lymphocyte count returns to the normal range after interruption of study drug.
- If a patient experiences excessive bone loss, defined as a loss at the lumbar spine or total hip of 7% or greater compared to baseline at any point in the trial.
- If a patient demonstrates:
 - Persistent elevations [$> 3 \times$ Upper Limit of Normal (ULN)] in aspartate aminotransferase (AST) or alanine aminotransferase (ALT) (2 consecutive readings at least 2 weeks apart) - OR -
 - Persistent elevations [$> 2 \times$ Upper Limit of Normal (ULN)] in total bilirubin (2 consecutive readings at least 2 weeks apart).
- If a patient begins a treatment regimen with a strong CYP3A4 inducer (e.g., rifampin [rifampicin], phenobarbital, barbiturates, carbamazepine, phenytoin, St. John's wort, nevirapine, efavirenz, etravirine) for a period longer than 6 months in duration.
- If a patient commences therapy with low-dose systemic estrogens for 6 months or more.
- If a patient begins treatment with bisphosphonates, strontium, or PTH, the SPONSOR must be contacted and blinded study therapy will likely be discontinued.

Patients will be followed for outcome through the end of the trial even if blinded study therapy is discontinued.

Subjects/patients may withdraw at any time or be dropped from the study at the discretion of the investigator should any untoward effects occur. In addition, a subject/patient may be withdrawn by the investigator or the SPONSOR if he/she violates the study plan or for administrative and/or other safety reasons. The investigator or study coordinator must notify the SPONSOR immediately when a subject/patient has been discontinued/withdrawn due to an adverse experience (telephone or FAX). When a subject/patient discontinues/withdraws prior to study completion, all applicable activities scheduled for the final study visit should be performed at the time of discontinuation. Any adverse experiences which are present at the time of discontinuation/withdrawal should be followed in accordance with the safety requirements outlined in Section 3.4 SAFETY MEASUREMENTS - DETAILS.

Product: MK-0822

27

Protocol/Amendment No.: 018-04

Subjects/patients who donate a blood sample for future genetic analyses may request that their sample be removed from storage and destroyed in accordance with the terms outlined in the informed consent for genetic analyses. Subjects/patients should be informed that withdrawal from the main study does not cause the withdrawal and destruction of the genetic sample. Requests for withdrawal and destruction of the genetic sample should be made in writing to the investigator.

